#### 7.4.2 Cardiovascular Responses

Summary statistics (n, mean, standard deviation, median, minimum and maximum) of HR and BP by treatment, cocaine dose, infusion session, and timepoint will be presented. Maximum, maximum change and time to maximum from pre-infusion during the first hour after each infusion will be summarized by treatment, cocaine dose, and infusion session.

The maximum value and maximum change from pre-infusion values will be analyzed using an analysis of covariance (ANCOVA) model to compare the treatment groups (SXC-2023 versus placebo). The ANCOVA model will include the baseline (i.e., prior to SXC-2023/placebo treatment) maximum value or the baseline maximum change from pre-infusion as a covariate. The analyses for the 20mg and 40mg cocaine infusions will be performed separately. Effects will be considered statistically significant at a two-sided  $p < 0.05$ .

The distribution of the maximum value and maximum change for HR and BP will be explored. If not deemed normal or if right skewed, an ANCOVA analysis will be performed on the log-transformed HR and BP maximum value and maximum change. If the log-transformed data distribution is not normal then a Wilcoxon rank sum test will be used to compare treatment groups.

Time to maximum value will be analyzed using a Kaplan-Meier estimator. A log-rank test will be used to compare the time to maximum value by treatment groups (SXC-2023 vs Placebo). The analyses for the 20mg and 40mg cocaine infusions will be performed separately. Effects will be considered statistically significant at a two-sided  $p < 0.05$ .

ECG parameters extracted from Holter and their changes from pre-infusion (mean of the 3 pre-infusion ECGs) will be presented with summary statistics by visit and timepoint. Changes in ECG intervals during saline infusion as compared to those taken during cocaine infusions will be also reported as summary statistics. A listing of clinically significant ECG changes will be presented.

Pulse will be summarized by infusion session, timepoint, and treatment group.

Clinically significant ECG values will be presented in listings.

A listing of repeated assessments will be presented.

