#### **2.2.2.2      Safety**

Intravenous (i.v.) cocaine administration spanning the doses proposed for use in this study (20 mg and 40 mg) has been previously investigated in human laboratory clinical trials (Johnson *et al.*, 1998; Walsh *et al.*, 1994). Johnson and colleagues conducted continuous non-invasive cardiovascular monitoring in eight healthy cocaine addicts receiving i.v. doses of cocaine 0.325 mg/kg or 0.650 mg/kg. They demonstrated dose dependent increases in pulse and mean arterial pressure following cocaine administration that peaked 5 minutes post-cocaine infusion with a maximal response being sustained for a further 15 and 35 minutes afterwards, respectively. Cocaine administration had no significant effect on peripheral oxygen saturation, and no clinical abnormalities of rhythm or conductivity were seen on ECG. These doses of cocaine (20 mg and 40 mg) and the method of single-dose i.v. cocaine administration as well as procedures for cardiovascular monitoring appear to be relatively safe for laboratory studies of healthy cocaine addicts with no pre-existing cardiovascular disease. Importantly, in a Phase 1 clinical trial study of fluoxetine, i.v. cocaine doses of 20 mg and 40 mg did not produce any adverse physiological or subjective reactions in 5 healthy adult male volunteers with histories of cocaine abuse (Walsh *et al.*, 1994). These doses of cocaine (20 mg and 40 mg i.v.) were also used in a recent drug-drug interaction study of cocaine and lorcaserin (NIDA, 2016). No severe AEs were reported in that study. Only one moderate AE was reported, a case of euphoria experienced subsequent to cocaine infusion and considered to be related to cocaine. The most frequent cocaine-related AEs experienced across the entire safety population (N=26) were euphoric mood (25 participants,

96%), abnormal feelings (11 participants, 42%), hyperhidrosis (10 participants, 38%), feeling hot (10 participants, 38%), tachycardia (6 participants, 23%), and paraesthesia (5 participants, 19%). These events coincided with cocaine infusion and were consistent with the risk profile of low-dose cocaine administration.

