#### **2.2.2.3      Pharmacokinetics and Metabolism**

The distribution half-life of cocaine from an i.v. dose is about 10 minutes and the elimination half-life of cocaine was found to be about 1 hour (50-80 minutes) by Jeffcoat *et al.*, 1989, although subsequently a half-life of about 4 hours was reported by Cone (1995).

Cocaine is primarily metabolized by esterases in the plasma and liver to inactive metabolites, benzoylecgonine (BE), ecgonine methyl ester and ecgonine (Stewart *et al.*, 1977; Kloss *et al.*, 1984; Dean *et al.*, 1991; Kolbrich *et al.*, 2006). A very small portion of cocaine is metabolized by hepatic microsomal enzyme CYP3A to an active metabolite, norcocaine (N-demethyl metabolite) (Ladona *et al.*, 2000); however norcocaine is a minor metabolite that accounts for only 2 to 6% of the administered cocaine dose (Inaba *et al.*, 1978). In the presence of ethanol, liver carboxylesterase catalyzes the ethyl transesterification of cocaine to form cocaethylene plus methanol (Dean *et al.*, 1991).

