### **3.2 Secondary**

1. To evaluate whether administration of SXC-2023 alters the pharmacokinetics (PK) of cocaine and/or its major metabolite, benzoylecgonine (BE).
2. To determine the PK of SXC-2023 administered at a dose of 800 mg once daily.
3. To evaluate whether SXC-2023 treatment alters the subjective effects of cocaine measured by Visual Analog Scales (VAS) and Brief Substance Craving Scale (BSCS).

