## 10.5 Cardiovascular Assessments During Infusion Sessions

Before and after each i.v. infusion, the participant's physiologic responses will be closely monitored using repeated HR, BP, and ECG readings, assessed in semi-supine position.

During the Screening Infusion Session 1, BP and HR will be recorded at the following nominal time points relative to the first infusion of the day: -30, -15, 5, 10, 15, 20, 25, 30, 45, 55, 65, 70, 75, 80, 85, 90, 105, 115, 125, 130, 135, 140, 145, 150, 165, 180, 210, 240, 270, 300, 330 and 360 minutes. Out of range BP and HR collected during the first 180 minutes post-dose will be repeated if deemed necessary by an investigator. Continuous cardiac monitoring with telemetry beginning approximately 60 minutes before the first infusion until 4 hours after the last cocaine infusion. Twelve-lead ECG measurements will be recorded at -30 minutes and at 5, 10, 15, 30, 45, 65, 70, 75, 90, 105, 125, 130, 135, 150, 165, 180, and 360 minutes after the first infusion. Study personnel and staff will monitor participants for at least 1 hour after each infusion. Times for collection of ECG and vital signs are nominal times  $\pm 3$  minutes for the first 30 minutes after the infusion and  $\pm 5$  minutes at all other time points. ECG then vital signs will be collected first when multiple assessments are scheduled at the same nominal time.

During the baseline and treatment infusions (Sessions 2 to 5), BP and HR will be recorded at the following time points relative to the first infusion of the day: -30, -15, 5, 10, 15, 20, 25, 30, 45, 55, 65, 70, 75, 80, 85, 90, 105, 120, 150, 180, 210, 240, 270, and 300 minutes. Out of range BP and HR collected during the first 180 minutes post-dose will be repeated if deemed necessary by an investigator. Continuous cardiac monitoring with telemetry beginning approximately 60 minutes before the first infusion until 4 hours after the second infusion. Twelve-lead ECG measurements will be recorded at -30 minutes and at nominal 5, 10, 15, 30, 45, 65, 70, 75, 90, 120, 150, 180 and 300 minutes after the first infusion. Times for collection of ECG and vital signs are nominal times  $\pm 3$  minutes for the first 30 minutes after the infusion and  $\pm 5$  minutes at all other time points. ECG then vital signs will be collected first when multiple assessments are scheduled at the same nominal time.

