#### **12.4.2 Vital Signs and ECG Changes**

Vital signs data (HR and BP) will be presented as summary statistics of maximum (max) absolute values, max change from baseline, and time to max value during the 1-hour period after each cocaine infusion. Data will be compared between groups and within groups by study day by Wilcoxon rank sum statistic. Effects will be considered statistically significant at a two-sided  $p < 0.05$ . In addition, summary statistics for vital signs at each study time point will also be presented. Changes in ECG intervals during saline infusion as compared to those taken during cocaine infusions will be reported as summary statistics. Clinically significant ECG changes will be presented as counts and percentages.

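### No formal between-arm test covers HR or BP after the first hour, so a prolonged cardiovascular response to cocaine is described but never formally compared

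*SAP*

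**What the plan says.** SAP 7.4.2 sets the HR and BP response measures: "Maximum, maximum change and time to maximum from pre-infusion during the first hour after each infusion will be summarized". Two kinds of between-arm test follow.

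- The maximum and the maximum change are "analyzed using an analysis of covariance (ANCOVA) model to compare the treatment groups (SXC-2023 versus placebo"), with a log-transformed ANCOVA or a Wilcoxon test on the same two measures as fallbacks.
- For the third measure, "A log-rank test will be used to compare the time to maximum value by treatment groups (SXC-2023 vs Placebo").

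Both are judged at two-sided p < 0.05, separately for 20 mg and 40 mg. Protocol 12.4.2 has the same limit. Its Wilcoxon comparison covers the maximum, the maximum change and the "time to max value during the 1-hour period after each cocaine infusion".

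Recording goes on much longer. Protocol 10.5 and SAP 5.1.2 end the HR and BP schedule for Sessions 2 to 5 with "105, 120, 150, 180, 210, 240, 270, and 300 minutes", counted from the first infusion. Both documents promise summary statistics at every timepoint, and SAP 7.4.2 gives them by treatment, cocaine dose and session. Neither plans an area, duration, repeated-measures or late-window comparison of HR or BP.

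SAP 7.5.2.6 compares cocaine CL and AUC between arms by ANCOVA. Cocaine PK is sampled only in Sessions 3 and 5, the 40 mg sessions.

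**The concern.** The primary objective is whether SXC-2023 and cocaine interact on the cardiovascular system. After a 60-second i.v. push, the peak is set mainly by dose and early distribution: "The distribution half-life of cocaine from an i.v. dose is about 10 minutes" (Protocol 2.2.2.3). Slower clearance shows mostly in how long the effect lasts. Altered cocaine PK is a stated question of the trial: "To evaluate whether administration of SXC-2023 alters the pharmacokinetics (PK) of cocaine" (Protocol 3.2).

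The protocol itself treats duration as part of the response. In the earlier monitoring study cited in Protocol 2.2.2.2, pulse and mean arterial pressure "peaked 5 minutes post-cocaine infusion with a maximal response being sustained for a further 15 and 35 minutes afterwards, respectively". The BP and HR stopping criteria in Protocol 9.10 also rest on values sustained for 5 minutes or more.

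If SXC-2023 lengthened the HR or BP response without much raising its peak, none of the planned HR/BP tests would be aimed at it. A late contrast chosen after seeing the timepoint tables would be post hoc.

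**Working it through.** **1. Readings inside and outside the tested window.** Post-infusion HR/BP times in Sessions 2 to 5, from the first infusion, are 5, 10, 15, 20, 25, 30, 45, 55, 65, 70, 75, 80, 85, 90, 105, 120, 150, 180, 210, 240, 270 and 300 minutes.

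- Cocaine first: 22 readings after cocaine, 8 of them within 60 minutes, the last at 300. Fourteen are untested.
- Cocaine second (subtract 60): 5, 10, 15, 20, 25, 30, 45, 60, 90, 120, 150, 180, 210 and 240. That is 14 readings, 8 of them within 60 minutes. Six are untested.
- Common to both orders up to 240 minutes: 5, 10, 15, 20, 25, 30, 45, 90, 120, 150, 180, 210 and 240, which is 13 timepoints.

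**2. Sample size.** The plan gives 20 randomised and 8 completers per arm, with no power, effect size or SD, so there is no figure to reproduce. By normal approximation, the standardised difference detectable with 80% power at 8 per arm is (1.96 + 0.84) × √(2/8) = 1.40 SD. A peak shift of a few percent is effectively undetectable.

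**3. Effect of halving clearance.** Protocol 2.2.2.3 gives a distribution half-life of about 10 minutes and elimination half-lives of about 1 hour (50–80 minutes) and, from a later source, about 4 hours. Assumed: a two-compartment bolus, effect proportional to concentration, coefficient ratio A/B of 1–4, effect lag of 0–3 minutes.

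C(t) = A·exp(−αt) + B·exp(−βt), with A + B = 1; k21 = Aβ + Bα; k10 = αβ/k21; k12 = α + β − k21 − k10.

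Example with A = B = 0.5, no lag, 60-minute half-life:

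- α = ln2/10 = 0.0693 and β = ln2/60 = 0.01155, so k21 = 0.0404, k10 = 0.0198 and k12 = 0.0206.
- Halving k10 to 0.0099 gives new exponents 0.0648 and 0.00618, with coefficients 0.416 and 0.584.
- C(5) goes from 0.825 to 0.867, up 5.1%.
- Area 0–240 = (A/α)(1 − exp(−240α)) + (B/β)(1 − exp(−240β)) goes from 47.8 to 79.5, up 66%.

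The same example with a 240-minute half-life (β = 0.00289): C(5) goes from 0.846 to 0.858, up 1.4%, and the area from 93.8 to 112.3, up 20%.

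Over the whole assumed range, with clearance halved:

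| Elimination half-life | First-hour peak | Area 0–240 min |
|---|---|---|
| 60 min | +5–12% | about +65–80% |
| 4 h | +1–4% | about +19–28% |

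Using the trapezoid on the 13 common timepoints leaves the area gains within these ranges. The scheduled time of the peak does not move, so the log-rank test does not help here.

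**4. Illustrative power.** Simulated ANCOVA with 8 per arm and the baseline session as covariate (assumed mean peak rise 20–30 units, reading SD 5–8, between-participant CV 30%), clearance halved, 60-minute half-life: about 6–13% for the maximum change and 10–49% for the 0–240 minute mean. With the 4-hour half-life, power for the 0–240 minute mean falls to about 7–16%. For a pure 1.4-fold rise in sensitivity the maximum does better, 25–53% against 9–19%.

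**The case against.** **Late readings are tabulated by arm.** Every HR and BP reading is summarised by treatment, dose, session and timepoint. With 8 completers per arm and no power basis, description is a defensible choice. This stands: the gap is the absence of a formal comparison. A reader might infer that the late data are discarded, or that a prolonged response would be invisible. SAP 7.4.2 supports neither reading.

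**Clearance is tested directly.** The PK ANCOVA covers cocaine CL and AUC, so a reader cannot infer that a clearance interaction would go untested. That stands for 40 mg. At 20 mg there is no PK comparison, and at either dose a longer cardiovascular effect without a PK change is not what that analysis measures.

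**The scenario is extreme.** Cocaine is cleared mainly by esterases, norcocaine accounts for 2–6% of the dose (Protocol 2.2.2.3), and the SXC-2023 IC50 for CYP3A4 exceeds 4000 µM (Protocol 2.2.1.4). Nothing in the documents suggests esterase inhibition, but nothing excludes it. Halved clearance is an illustration, not a forecast.

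**The effect model is too simple.** The sustained maximum in Protocol 2.2.2.2 runs to about 20 and 40 minutes, inside the first hour, while the model at a 60-minute half-life has fallen to 23–54% of maximum by 40 minutes. Lags of 10–20 minutes hold the plateau better, though they peak later than 5 minutes, and raise the first-hour peak by 14–25%. So the peak is less blind than step 3 suggests, although the 0–240 minute area still rises more.

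**The added measure has modest power.** This stands, and it is a reason to report an estimate and interval as supportive evidence and not to rely on a p-value.

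**Conclusion.** The gap is real and limited. All formal between-arm HR/BP tests use the first-hour maximum, maximum change or time to maximum. A response prolonged beyond that, recorded to at least 240 minutes after cocaine, appears only in descriptive summaries.

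The benefit of a longer window depends on the half-life. It is large at 60 minutes (peak 5–12% against area about 65–80%) and modest at 4 hours (1–4% against about 19–28%). Both results assume halved clearance and an effect that follows concentration. The power figures rest on assumed variability.

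This is a cheap improvement to the answer on the primary objective. It does not invalidate the planned analysis, and the maximum remains the better measure for a change in sensitivity. A reader might also infer that low values are overlooked, but the minimum HR and BP by arm and timepoint are already planned, so no separate tabulation is needed.

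**What to change.** In SAP 7.4.2 and Protocol 12.4.2, add one supportive measure for each of HR, SBP and DBP at each cocaine dose: the time-weighted mean change from pre-infusion over 0–240 minutes after the start of the cocaine infusion.

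- Compute it by the trapezoid rule on the 13 timepoints common to both infusion orders, with the same pre-infusion reference as the maximum change.
- Analyse it with the planned ANCOVA, with the matching Session 2 (20 mg) or Session 3 (40 mg) value as covariate.
- Include infusion order as a factor or in a sensitivity analysis, since cocaine-first participants receive saline at 60 minutes, inside the window.
- Report the estimate and confidence interval beside the maximum, not in its place, and label it supportive.

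The cost is SAP and protocol wording and a few derived variables, with no new data. It adds 3 parameters × 2 doses = 6 unadjusted comparisons to the existing 3 measures × 3 parameters × 2 doses = 18 (counting BP as SBP and DBP), so some extra chance findings must be expected.

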### **2.2.1.4      Pharmacokinetics (PK) and Metabolism**

In the single oral dose Phase I study (PRO-101), the pharmacokinetics (PK) of SXC-2023 in healthy volunteer participants were observed using doses ranging from 50 mg to 1600 mg. Under fasted conditions, the mean geometric peak plasma concentration ( $C_{max}$ ) of SXC-2023 ranged from 758.2 ng/mL for the 50 mg dose to 33,700 ng/mL for the 1600 mg dose and occurred approximately 2.5 to 4.0 hours post-dose ( $T_{max}$ ). The elimination half-life ( $T_{1/2}$ ) for SXC-2023 for the tested dose range (50 mg to 1600 mg) was 3 to 6 hours. Administration of SXC-2023 (800 mg) with a high-fat meal lowered mean  $C_{max}$  and delayed  $T_{max}$  by ~3.5 hours compared to the same dose administered under fasted conditions. For doses ranging from 50 mg to 1600 mg, the area under the concentration-time curve extrapolated to infinity ( $AUC_{0-\infty}$ ) was 3213 ng\*hr/mL to 239,700 ng\*hr/mL. Following the consumption of a high-fat meal, the overall exposure ( $AUC_{0-\infty}$ ) was slightly increased following administration of SXC-2023 (Investigator's Brochure, 2024).

The PK of SXC-2023 in a multiple ascending dose study was conducted at 200 mg QD, 400 mg QD, 800 mg QD, and 400 mg BID. The  $C_{max}$  of SXC-2023 (at Day 14, under fasted conditions) ranged from 7990 ng/mL (200 mg QD dose) to 30,540 ng/mL (800 mg QD dose). The median

$T_{\max}$  ranged from 2 to 6 hours for the tested doses. For the 200 mg to 800 mg dose range, the  $T_{1/2}$  of SXC-2023 was ~3.4 to 5.2 hours and 9.4 to 11.7 hours on Days 1 and 14, respectively. Following single and multiple doses of SXC-2023 (200 mg to 800 mg, fasted conditions), the PK parameters for  $AUC_{0-t}$ ,  $AUC_{0-\infty}$ , and  $C_{\max}$  was dose proportional to AUC and  $C_{\max}$  on Day 1 and Day 14.

Overall, the food effect of SXC-2023 (800 mg with a high-fat meal) resulted in a lower, delayed  $C_{\max}$ , a slight increase of AUC, and a delayed  $T_{\max}$  (Investigator's Brochure, 2024).

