### 9.7 Treatment Period (Days 3-9)

Participants will begin receiving 800 mg SXC-2023 or placebo once daily (QD, mornings) from Day 3 to Day 9.

The following assessments will be performed daily before dosing:

- adverse events/serious adverse events
- concomitant medications
- vital signs (HR and BP) prior to dosing with SXC-2023
- safety laboratory tests (hematology, clinical chemistry, and urinalysis) will be collected on Day 6.
- blood for SXC-2023 PK will be collected on Day 9 approximately 15 minutes prior to the morning dose and up to 48 hours post-Day 9 dose.

Blood collections will be performed within  $\pm 1$  minute for the first 30 minutes after the infusion and  $\pm 5$  minutes at all other time points.

The treatment infusion sessions (Sessions 4 and 5 – Study Days 8 and 9, described below) provide cardiovascular effects, subjective responses, and PK data for SXC-2023 at steady state. The schedule of assessments is shown in [Table 4](#). The times are nominal times with a window of  $\pm 1$  minute for PK blood samples for the first 30 minutes after the infusion and  $\pm 5$  minutes at all other time points. When multiple assessments are scheduled at the same time, they should be performed in the order of ECG, vital signs, VAS, then blood draws.

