#### 9.7.1 Infusion Session 4 (Day 8)

The infusion session is performed as described previously; cocaine (20 mg) and saline will be administered in the same order in which they were administered during Session 2. The participant's semi-supine blood pressure must be  $\leq 140$  mm Hg (systolic) and  $\leq 90$  mm Hg (diastolic), heart rate must be  $\leq 100$  beats per minute taken in the half-hour prior to receiving any cocaine infusion. If blood pressure or heart rate is elevated, it may be repeated one time to determine if the participant meets these criteria to receive an infusion. The participant's ECG taken in the half-hour (-30 minutes) prior to receiving any cocaine infusion must not have any clinically significant abnormal arrhythmia or interval changes. Pregnancy test will be done and must be negative before infusion.

SXC-2023 will be administered three hours prior to the first cocaine/saline infusion of the day.

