Once a participant has been determined to be eligible, the participant will be randomized on Day -1 to receive either SXC-2023 or placebo. On Days 1 and 2, participants will receive baseline infusions of saline and cocaine (Day 1/Infusion Session 2: 20 mg cocaine; Day 2/Infusion Session 3: 40 mg cocaine). The order of the saline and cocaine infusions will be randomized for each session. The participants will receive either SXC-2023 or matched placebo once a day every morning from Days 3 to 9. On Day 8, participants will receive cocaine 20 mg infusion (Infusion Session 4) and on Day 9 participants will receive cocaine 40 mg (Infusion Session 5). Each cocaine infusion will be preceded or followed by saline i.v. infusion. The first infusion on Days 8 and 9 will begin approximately 3 hours after SXC-2023 800 mg or placebo. Each infusion will consist of a 2 mL i.v. push and will be administered 60 minutes apart. The order of the saline and cocaine infusions for each participant for Infusion Sessions 4 and 5 will be the same as the randomized order for Infusion Sessions 2 and 3, respectively. The participants will be discharged from the research clinic on Day 11, 2 days after the last infusion of cocaine (Infusion Session 5), and will have a telephone follow-up call between 7 and 10 days after clinic discharge.

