#### **5.1.2 Cardiovascular and Blood Pressure Assessments**

Before and after each i.v. infusion, the participant's physiologic responses will be closely monitored using repeated HR, BP, and ECG readings assessed in semi supine position.

During the Screening Infusion Session 1, BP and HR will be recorded at the following nominal time points relative to the first infusion of the day: -30, -15, 5, 10, 15, 20, 25, 30, 45, 55, 65, 70, 75, 80, 85, 90, 105, 115, 125, 130, 135, 140, 145, 150, 165, 180, 210, 240, 270, 300, 330 and 360 minutes. Out of range BP and HR collected during the first 180 minutes post-dose will be repeated if deemed necessary by an investigator. Continuous cardiac monitoring with telemetry will begin approximately 60 minutes before the first infusion and will end 4 hours after the last cocaine infusion. Twelve-lead ECG measurements will be recorded at -30 minutes and at 5, 10, 15, 30, 45, 65, 70, 75, 90, 105, 125, 130, 135, 150, 165, 180, and 360 minutes after the first infusion. Study personnel and staff will monitor participants for at least 1 hour after each infusion. Times for collection of ECG and vital signs are nominal times  $\pm$  3 minutes for the first 30 minutes after the infusion and  $\pm$  5 minutes at all other time points. ECG, then vital signs will be collected first when multiple assessments are scheduled at the same nominal time.

During the baseline and treatment infusions (Sessions 2 to 5), BP and HR will be recorded at the following time points relative to the first infusion of the day: -30, -15, 5, 10, 15, 20, 25, 30, 45, 55, 65, 70, 75, 80, 85, 90, 105, 120, 150, 180, 210, 240, 270, and 300 minutes. Out of range BP

and HR collected during the first 180 minutes post-dose will be repeated if deemed necessary by an investigator. Continuous cardiac monitoring with telemetry beginning approximately 60 minutes before the first infusion until 4 hours after the second infusion. Twelve-lead ECG measurements will be recorded at -30 minutes and at nominal 5, 10, 15, 30, 45, 65, 70, 75, 90, 120, 150, 180 and 300 minutes after the first infusion. Times for collection of ECG and vital signs are nominal times  $\pm 3$  minutes for the first 30 minutes after the infusion and  $\pm 5$  minutes at all other time points. ECG, then vital signs will be collected first when multiple assessments are scheduled at the same nominal time.

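### On Days 8 and 9 both derived ECG contrasts use references taken on SXC-2023, so the drug's own effect on QTcF is left to unpaired descriptive values

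*SAP*

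**What the plan says.** **Dose timing.** For Session 4, Protocol 9.7.1 states: "SXC-2023 will be administered three hours prior to the first cocaine/saline infusion of the day". Protocol 9.7.2 says the same for Session 5, and SAP 4.1 agrees: "The first infusion on Days 8 and 9 will begin approximately 3 hours after SXC-2023 800 mg or placebo". Protocol Table 4 and SAP Table 4-5 place the dose at -180 minutes.

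**Pre-infusion readings, Sessions 2 to 5.** HR and BP are taken at "time points relative to the first infusion of the day: -30, -15, 5, 10, 15, 20, 25, 30, 45, 55" and later times (SAP 5.1.2). For the ECG, Protocol 10.5 has "Twelve-lead ECG measurements will be recorded at -30 minutes and at nominal 5, 10, 15" and later times, so one scheduled ECG time precedes the first infusion. Protocol Table 2 has ECGs on Days 1, 2, 8, 9 and 11 and none on Days 3 to 7. Daily pre-dose checks in Protocol 9.7 include "vital signs (HR and BP) prior to dosing with SXC-2023" but no ECG.

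**Analysis (SAP 7.4.2).** For HR and BP, two outcomes are tested by ANCOVA. One is the maximum value; for the other, "maximum change from pre-infusion values will be analyzed using an analysis of covariance (ANCOVA) model to compare the treatment groups". Each is adjusted for its own pre-treatment counterpart. For the ECG parameters, "their changes from pre-infusion (mean of the 3 pre-infusion ECGs) will be presented with summary statistics by visit and timepoint". The only other derived ECG contrast compares saline with cocaine infusions, also by summary statistics. No between-arm ECG comparison and no change from Day 1 or Day 2 is planned.

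**Exposure.** After single fasted doses the SXC-2023 peak "occurred approximately 2.5 to 4.0 hours post-dose" (Protocol 2.2.1.4). The multiple-dose median Tmax is 2 to 6 hours, and the half-life is 3.4 to 5.2 hours on Day 1 and 9.4 to 11.7 hours on Day 14.

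**The concern.** A change score shows only what happens after its reference. If the reference is read when SXC-2023 is near its peak, any shift the drug itself produces in QTcF sits on both sides of the subtraction and drops out. The saline-versus-cocaine contrast behaves the same way, because on Days 8 and 9 both infusions are given on drug, 60 minutes apart.

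QTcF is a named primary endpoint. The first on-treatment ECG is itself the reference, and the next ECG after Day 9 is at discharge on Day 11, about 48 hours after the last dose. A table showing equal QTcF change in the two arms could therefore be read as showing that SXC-2023 does not move QTcF, which that table cannot show.

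**Working it through.** **1. Timing.** Hours after dose = (minutes from first infusion + 180) / 60.

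| Event | Minutes | Hours after dose |
|---|---|---|
| First infusion (plan's figure: about 3 h) | 0 | 3.00 |
| Pre-infusion ECG, HR, BP | -30 | 2.50 |
| Second HR, BP reading | -15 | 2.75 |
| Last ECG before second infusion | 45 | 3.75 |
| Hour after first infusion | 0 to 60 | 3 to 4 |
| Hour after second infusion | 60 to 120 | 4 to 5 |

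The plan's 3 hours is reproduced, and 2.5 hours lies within both stated Tmax ranges. The SAP gives no times for its three pre-infusion Holter ECGs. If they come from the telemetry period, which starts 60 minutes before the first infusion, the earliest is (-60 + 180)/60 = 2 hours after the dose.

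**2. What each contrast keeps.** Write d(t) for the drug's own effect t hours after dosing, c for the cocaine response and i for the interaction.

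- Change from same-day pre-infusion, SXC-2023 minus placebo: i + d(window) - d(2.5 h). A constant d cancels exactly.
- Cocaine minus saline infusion, SXC-2023 minus placebo: i + d(one window) - d(the other). A constant d cancels again.
- Day 8/9 minus Day 1/2 at -30 minutes, SXC-2023 minus placebo: d(2.5 h), because Days 1 and 2 precede the first dose.
- Day 8/9 minus Day 1/2, time-matched after infusion: d(window) + i. The infusion order is the same in the paired sessions, so c cancels between arms.

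**3. How much cancels if d follows concentration.** Assume one-compartment oral kinetics at steady state, dosing every 24 h and no absorption lag: C(t) proportional to e^(-kt)/(1 - e^(-24k)) - e^(-at)/(1 - e^(-24a)), with k = ln 2 / half-life and a solved to give the stated Tmax.

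| Half-life | Tmax | C(2.5 h) / mean C, 3-4 h | C(2.5 h) / mean C, 4-5 h |
|---|---|---|---|
| 9.4 h | 2 h | 1.06 | 1.13 |
| 9.4 h | 6 h | 0.91 | 0.86 |
| 11.7 h | 2 h | 1.05 | 1.11 |
| 11.7 h | 6 h | 0.92 | 0.88 |

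The share left in the change score is 1 minus the ratio: from 1 - 1.13 = -0.13 to 1 - 0.86 = +0.14 of the effect present in the window. With the Day 1 half-lives the ratios span 0.83 to 1.33, leaving -0.33 to +0.17 (a Tmax of 6 h cannot be reached with a 3.4 h half-life). For saline versus cocaine, mean levels in the two windows differ by a factor of 0.95 to 1.07 at the Day 14 half-lives.

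**4. HR and BP.** The SAP's ANCOVA was simulated with 10 per arm and assumed SDs: 8 between participants, 5 for the pre-infusion reading, 8 for the cocaine response and 4 at the maximum. With a pure drug effect of 10 and no interaction, maximum value estimates 10.0 (rejection rate 0.96) and maximum change estimates 0.1 (0.04). The pre-treatment maximum-change covariate does not restore the loss, but the maximum-value analysis does not suffer it.

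**5. What pairing gains for QTcF.** Let s be the SD of QTcF at one time and r its Day 1/2 to Day 8/9 correlation; neither is in the documents. The variance is s² for an absolute value, 2s²(1 - r) for a change, and about s²(1 - r²) when adjusted for the earlier value. The 95% half-width for the arm difference at n = 10 per arm is t × √(2/n × factor) × s:

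- Absolute: 2.101 × √0.2 = 0.94 s.
- Adjusted, r = 0.5: 2.110 × √(0.2 × 0.75) = 0.82 s.
- Adjusted, r = 0.8: 2.110 × √(0.2 × 0.36) = 0.57 s.

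A plain change gains only if r exceeds 0.5, so the adjusted form is the safer choice.

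**The case against.** The primary objective is the interaction of SXC-2023 with cocaine. If the drug effect is purely additive, a null difference in change from an on-drug reference is the right answer to that question. This stands: the same-day change is a legitimate measure and should stay.

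Nor is the drug's own QTcF effect absent from the outputs. SAP 7.4.2 summarises ECG values as well as changes, SAP 7 presents all data by treatment group, and the arms are randomised. QTcF at -30 minutes on Day 8 or 9 can therefore be compared between arms. Among participants with both visits, the mean change from Day 1/2 is simply the difference of two tabulated means. This stands too. What cannot be recovered from those tables is the spread of the within-participant change, and hence a confidence interval, which matters with 8 to 10 participants per arm. The absolute QTcF stopping criteria and the listings of clinically significant values catch large individual values, not a moderate shift in the mean.

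The kinetic sketch is also open to challenge. It assumes that effect follows concentration and that there is no lag. The capsules are enteric and given before breakfast, and the protocol reports that a high-fat meal delays Tmax by about 3.5 hours. A true absorption lag would leave more of the effect in the change score.

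**Conclusion.** The point holds for QTcF. Both derived ECG contrasts in SAP 7.4.2 are within-day and on drug, so they remove a steady SXC-2023 effect entirely and, under the sketch above, most or all of a concentration-driven one. That effect would then appear only in unpaired descriptive values and listings. The timing is exact from the schedule. The size of the loss is unknown, because the documents report no size for any SXC-2023 effect on QTcF.

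A reader might infer that SXC-2023's own effect is subtracted from the whole cardiovascular safety result. The documents do not support that. Absolute maximum HR and BP are tested with the pre-treatment maximum as covariate, and absolute HR and BP are summarised by arm, session and time point. A reader might also infer that the Day 8 and 9 pre-dose vital signs would serve as an off-drug baseline. They follow five and six doses respectively, and in the same sketch (half-life 9.4 to 11.7 h, Tmax 2 to 6 h) the trough is 0.22 to 0.47 of the level at 3.5 hours.

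**What to change.** In SAP 7.4.2:

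- Keep the ECG change from same-day pre-infusion, but label it as the added cocaine response on treatment.
- Add, by arm, the within-participant QTcF change from the drug-free session at the same cocaine dose (Day 1 for Day 8, Day 2 for Day 9), both at -30 minutes and time-matched after infusion.
- Report the SXC-2023 minus placebo difference with its confidence interval, for example from a model of Day 8 or Day 9 QTcF adjusted for the matching Day 1 or Day 2 value.
- State the clock times of the three pre-infusion Holter ECGs, and which reading is the reference for the second infusion.
- Optionally, add the same Day 1/2-referenced change for HR and BP. Do not use the Day 8 and 9 pre-dose vital signs as an off-drug baseline.

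The paired comparison uses ECGs already scheduled. The cost is SAP wording and a few more derived variables and tables. The small downside is a reference 7 days old, somewhat noisier than a same-day one, which adjusting for the earlier value rather than subtracting it helps to contain.
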